29 a "morselized, flowable tissue allograft derived from amniotic tissues. Amniotic tissues have been shown
30 to support soft tissue repair, reduce inflammation and minimize scar tissue formation".^{6,7}

31

32 This study will compare corticosteroid injection to BioDRestore injection in patients with significant
33 (Kellgren-Lawrence grade 3-4) knee osteoarthritis. Our hypothesis is that BioDRestore will result in
34 better outcomes than corticosteroid when injected intra-articularly in patients with knee OA.

35

36 **2. Study Endpoints**

37

38 Primary Endpoint

- 39 • Visual Analog Score (VAS), VR-12, Lysholm, SANE and Knee Injury and Osteoarthritis
40 Outcome Score (KOOS) at the 6-week, 3-month, 6-month, and 12-month post-injection time
41 periods.

42

43 Secondary Endpoints

- 44 • Inflammatory markers at 6-months post-injection.

45

46 **3. Subject Recruitment and Screening**

47

48 *Screening*

49 Patients who present with osteoarthritis of the knee and are recommended for a knee
50 injection will be screened for inclusion into the study. Following discussion of the
51 study between the patient and the treating physician, the patient will be given the
52 opportunity to move forward with the informed consent process.

53

54 *Enrollment*

55 The subject will be considered enrolled once voluntary informed consent has been
56 given, and the form has been signed and dated by all required parties.

57

58 *Randomization*

59 Subjects will be randomized to a treatment arm (corticosteroid or BioDRestore injection)
60 using a 1:1 ratio. Once study eligibility has been confirmed, the study coordinator or
61 designee will randomize the subject to a treatment arm. The treatment for each subject
62 will be assigned through the study database.

63
64
65
66
67
68
69
70
71
72
73
74
75
76
77
78
79
80
81
82
83
84
85
86
87
88
89
90
91
92
93
94
95
96
97
98
99
100
101
102
103
104
105
106
107
108
109
110
111
112

Blinding

Study subjects and investigators will be blinded to the treatment assignment for the duration of the study to reduce the risk of bias. The research coordinator will provide the randomization to the investigator’s medical assistant (MA) prior to treatment in order for the MA to assist with preparation of the injection.

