336 concerning the effect per FDA and/or IRB requests.
337

338 339 **9. Source Documentation**

340 Investigators are responsible for obtaining and maintaining complete subject health information in the
341 medical record for each subject and each assessment in the protocol (source documents). Source
342 documents include all information in original records and certified copies of original records of clinic
343 findings, observations or other activities in the study necessary for the reconstruction and evaluation
344 of the trial. Source data are contained in source documents (e.g., hospital records, clinic and office
345 charts, memoranda, dispensing records, subject questionnaires, clinic evaluation transcriptions,
346 operative notes, x-rays, radiology reports, blood collection and shipment records, research subject
347 files, etc.)
348

349 **10. Disclosure of Data and Data Security**

350 351 *Data Security and Confidentiality*

352 The clinical data obtained in this study will be kept private. In any sort of published
353 report, there will be no identifying information. Records for this study may be reviewed

354 by the IRB and/or other government agencies may inspect and photocopy all medical
355 records applicable to involvement in this study.
356

357 Participating subjects will be asked to sign a consent form that includes an authorization
358 to use and/or disclose personal health information. Subjects are free to refuse
359 authorization to transfer personal information. If the subject chooses not to agree to this
360 authorization, the subject is not eligible to participate in the study. Personal information
361 (including sensitive personal health information, such as medical history) if relevant to
362 the study will be reviewed, collected in a computer database, stored in electronic or
363 manual files, audited, and / or otherwise processed by the investigator, regulatory
364 agencies, and other persons and/or agencies as required by law or allowed by applicable
365 regulations.

366 **11. Statistical Procedures**

367 **11.1 Sample Size Estimate**

368
369 To determine sample size, we powered the study (a-priori) for the primary outcome measures of VAS,
370 VR-12, KOOS, Lysholm, and SANE scales at baseline, 6-week, 3-month, 6-month, and 12-month post-
371 injection time periods. Assuming normal distributions among the 2 independent groups' 5 time-points for

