372 2 groups and five outcome measures, and assuming an effect size of 0.20 (small) based on between group
373 differences we constructed a sample size estimation using a Multivariate Analysis of Variance
374 (MANOVA). Measuring global effects, with an expected 80% power, and a standard error of probability
375 of 0.05, we estimate the need for a minimum sample size of 70 for statistical significance (~35 per group).
376 To account for a 20% drop-out rate, a sample size of 84 subjects will be recruited. We will employ
377 intention to treat and a chains equation, multiple imputation method in which we will assign predictor,
378 structural and impute variables. Further, we will not oversample characteristics within each group for
379 drop-outs.
380
381

382 **11.2 Data Analyses**

383
384 Descriptive statistics will be used to describe both groups at baseline. Appropriate tests of differences will
385 be used to compare baseline differences in descriptive statistics, pain, range of motion, etc., between the
386 two groups (e.g., t-tests and chi-square). Adverse events, including severity of these events will be
387 captured and compared between the two groups. A Multivariate Analysis of Variance (MANOVA) will
388 be used to measure differences between the targeted outcome measure at each of the given timepoints
389 (baseline, 6-week, 3-month, 6-month, and 12-months post-injection time periods). A MANOVA
390 investigates the effects of a categorical predictive variable (groups) on 2 or more continuous outcomes,
391 which are correlated and represented by a vector of dependent variables. For all analyses, a p value of
392 <0.05 will be considered statistically significant.
393
394
395
396
397

398 **12. Bibliography**

- 399 1. Divine J, Zazulak B, Hewett TE. Viscosupplementation for knee osteoarthritis. Clin Orthop Rel
400 Res. 2006; 455:113-122.
- 401 2. Dawson J, Linsell L, Zondervan K, et al. Epidemiology of hop and knee pain and its impact on
402 overall health status in older adults. Rheumatology. 2004; 43:497-504.
403

404 3. Laupattarakasem W, Laopaiboon M, Laupattarakasem P, Sumananont C. Arthroscopic
405 debridement for knee osteoarthritis (Review). Cochrane Collaboration. Issue 4, 2009.
406 4. Younes M, et al. Systemic effects of epidural and intra-articular glucocorticoid injections in
407 diabetic and non-diabetic patients. *Joint Bone Spine*. 2007, 74(5): 472-6.

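### Section 11.1 does not name the metric of its effect size of 0.20; in the MANOVA described, 70 subjects follow if it is f-squared, a multivariate distance of about 0.89 that the label small misdescribes

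*Combined protocol and SAP*

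**What the plan says.** Section 11.1 (Sample Size Estimate) describes a MANOVA calculation that assumes "2 groups and five outcome measures, and assuming an effect size of 0.20 (small) based on between group" differences. The remaining inputs are "MANOVA). Measuring global effects, with an expected 80% power, and a standard error of probability" "of 0.05, we estimate the need for a minimum sample size of 70 for statistical significance (~35 per group"). I read the oddly named probability of 0.05 as alpha. The same section also mentions five time points: "injection time periods. Assuming normal distributions among the 2 independent groups' 5 time-points for" two groups and five outcomes.

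Section 11.2 (Data Analyses) plans a MANOVA that will "be used to measure differences between the targeted outcome measure at each of the given timepoints", and explains that the method "investigates the effects of a categorical predictive variable (groups) on 2 or more continuous outcomes". It describes those outcomes as correlated.

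Neither section names the effect-size index, gives a standard deviation or a correlation, or translates 0.20 into a difference on any scale. The hypothesis in Section 1 (Background) is that BioDRestore gives "better outcomes than corticosteroid when injected intra-articularly in patients with knee OA".

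**The concern.** In a MANOVA an effect size of 0.20 can be f, f-squared, Pillai's V or a Mahalanobis distance D. The required sample size differs more than twenty-fold across these. A reader who meets 0.20, the word small and a reference to between-group differences will probably think of a fifth of a standard deviation, and will conclude that the trial has 80% power for differences of that size.

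If the calculation used f-squared, the effect it was built on is much larger than that. A non-significant MANOVA could then be taken as evidence against small differences between BioDRestore and corticosteroid that the test had little chance of detecting.

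**Working it through.** **Inputs from Section 11.1:** 2 groups, p = 5 outcomes, global MANOVA test, power 0.80, alpha 0.05, effect size 0.20, N = 70 rising to 84 for drop-out. Allocation is 1:1 (Section 3, Randomization). **Assumed, because not given:** the correlation between scales (a common value ρ from 0 to 0.9) and the pattern of shifts.

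**Formula.** With two groups the global test is Hotelling's T-squared. It refers to F with p and N − p − 1 degrees of freedom and noncentrality λ = N·f². With equal arms f² = D²/4, where D² = d′R⁻¹d, d is the vector of standardised differences and R is the correlation matrix.

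**1. Reproducing 70.** With f² = 0.20 and N = 70, λ = 70 × 0.20 = 14 on 5 and 64 degrees of freedom. Power is 0.801; at N = 69 it is 0.794. The minimum is therefore 70, as stated. (With λ = (N − 2)·f² the answer is 72.)

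**2. Other meanings of 0.20 in the same MANOVA.**

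| 0.20 read as | f² | N for 80% power | Power at N = 70 |
|---|---|---|---|
| f-squared | 0.20 | 70 | 0.801 |
| Pillai V | 0.20/0.80 = 0.25 | 58 | 0.891 |
| f | 0.04 | 327 | 0.194 |
| D | 0.04/4 = 0.01 | 1,289 | 0.080 |

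For f = 0.20 the power at N = 84 is 0.231. With f² = 0.20 and 4, 20 or 25 responses instead of 5, the minimum N is 65, 122 or 135.

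**3. What f² = 0.20 means.** D = 2·√0.20 = 0.894. For equal shifts d on all five scales with common correlation ρ, D² = 5d²/(1 + 4ρ). Setting D² = 0.80 gives d = √(0.80·(1 + 4ρ)/5):

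- ρ = 0: 0.40 SD
- ρ = 0.3: 0.59 SD
- ρ = 0.5: 0.69 SD
- ρ = 0.8: 0.82 SD

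**4. Illustration: 0.20 SD on all five scales in the direction of benefit, one time point.** Here f² = 0.05/(1 + 4ρ).

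| ρ | f² | Power at 70 | Power at 84 |
|---|---|---|---|
| 0 | 0.0500 | 0.237 | 0.286 |
| 0.3 | 0.0227 | 0.125 | 0.144 |
| 0.5 | 0.0167 | 0.103 | 0.116 |
| 0.8 | 0.0119 | 0.086 | 0.095 |
| 0.9 | 0.0109 | 0.083 | 0.091 |

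Simulation at 35 per arm (20,000 runs) agrees: 0.239 at ρ = 0, 0.084 at ρ = 0.9, and 0.80 when D² = 0.80.

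**5. Can a different model return 70?** Yes, with f = 0.20 in a repeated-measures model.

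- Between-group test: λ = f²·N·m/(1 + (m − 1)ρ), with m time points and ρ now the correlation between them. With m = 5 and ρ = 0.18, λ = 0.04 × 70 × 5/1.72 = 8.14, and the minimum N is 70. This holds only for ρ of about 0.177 to 0.183; at ρ = 0.5 the minimum is 120.
- Group-by-time interaction: λ = f²·N·m/(1 − ρ). With m = 4 and ρ = 0 the minimum is 70; at ρ = 0.5 it is 36.

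**The case against.** **The arithmetic is not wrong.** That is right. Under f-squared the stated 70 is exact. A reader might infer a miscalculated sample size; the documents do not support that.

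**The protocol never says 0.20 SD.** Also right. A reader might infer that it claims 80% power for 0.20 SD per scale. It does not, so the figures in step 4 illustrate a likely misreading and do not refute a stated claim. What stands is that the label invites the misreading and nothing in the plan prevents it.

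**The model is open.** Section 11.1 mentions five time points, and Section 11.2 speaks of the outcome measure in the singular. A repeated-measures calculation with f = 0.20 is possible, so f-squared remains an inference. It is the simpler one, because it needs no unstated correlation. If f = 0.20 was used, the planned five-outcome MANOVA has only 19% power at 70 for that effect, so Section 11.1 needs correcting in that case too.

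**The low power does not cover every pattern of 0.20 SD.** This stands, and it limits the point in three ways.

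- *Unequal correlations.* Take 0.20 SD on scales 1 to 3 and none on 4 and 5, with r12 = 0.58, r13 = 0.44, r14 = 0.89, r15 = 0.60, r23 = 0.39, r24 = 0.65, r25 = 0.75, r34 = 0.60, r35 = 0.76, r45 = 0.67. Then D² = 0.902 and power at 70 is 85%. Such matrices were rare in a random search (under 1%), but they rule out a general statement.
- *Coding.* VAS is a pain score, so benefit presumably lowers it. If one scale moves against the other four after coding for benefit, power at ρ = 0.9 is 96%, not 8%.
- *One time point.* Section 11.2 plans a test at each. If the four follow-up tests were independent (an extreme assumption), the chance of at least one significant result would be 1 − (1 − 0.237)⁴ = 66% in place of 24%.

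**The harm is speculative.** In part. The plan states a superiority hypothesis and proposes no conclusion of equivalence. The risk lies in how a null result is read.

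**Conclusion.** The point holds as a reporting defect that should be fixed: Section 11.1 attaches 80% power to an effect size whose metric is not named, and its label does not fit the calculation that reproduces 70. Of the four metrics checked in the five-outcome MANOVA, only f-squared gives 70. The design effect is then a distance of about 0.89. Under equal shifts and equal correlations of 0 to 0.8, that is roughly two to four times 0.20 SD on every scale.

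Confidence is high that the metric is unnamed and that f-squared reproduces 70. It is lower that the sponsor used f-squared. The 8% to 24% range rests on equal 0.20 SD benefits on all five scales, equal correlations of 0 to 0.9, and a single time point.

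A reader might go further and infer that the study as a whole lacks 80% power for any 0.20 SD pattern in the direction of benefit. The documents give no correlations, shift pattern or cross-time success rule from which to conclude that, and the 85% example contradicts it as a general claim.

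**What to change.** Keep the sample size, test, alpha and endpoints.

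1. Check the sponsor's own calculation, and name the effect-size metric and the model in Section 11.1.
2. If it was MANOVA f-squared = 0.20, delete the label small. State D of about 0.89 and the implied per-scale differences (0.40, 0.59, 0.69 and 0.82 SD at correlation 0, 0.3, 0.5 and 0.8), with the assumptions beside them: equal shifts, equal correlations, and scales coded so that higher means benefit. Add that under those assumptions, with correlations of 0 to 0.9, power for 0.20 SD on all five scales at N = 70 is about 8% to 24% per time point. Do not add a general denial of power for every 0.20 SD pattern.
3. If another metric or model was used, show that calculation with its correlation, and restate the power of the planned five-outcome MANOVA (for f = 0.20, 19% at 70 and 23% at 84).

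The cost is one check and a few sentences, with no extra subjects. The downside is that the stated sensitivity becomes less favourable.

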3.3. Withdrawal of Subjects from Study

Voluntary Withdrawal by Subject

Study participation is voluntary and subjects may withdraw at any point during the study. If a subject withdraws from the study, the investigator will make all reasonable efforts to determine the reason for the subject’s withdrawal and will document the reason on the applicable form and in the patient’s medical record. After a subject withdraws from the study, no effort will be made to replace or follow the subject. However, the subject will still be offered clinical management of their knee condition.

Withdrawal by Investigator

The investigator may withdraw subjects from the study for many reasons, including but not limited to the following:

- Occurrence of a serious adverse event
- Investigator’s discretion to withdraw subject for safety reasons
- Subject noncompliance with visits and/or assessments
- Subject is lost to follow-up (as defined below)

113
114
115
116
117
118
119
120
121
122
123
124
125
126
127
128
129
130
131
132
133
134
135
136
137
138
139
140
141
142
143
144
145
146
147
148
149
150
151
152
153
154
155
156
157
158
159
160
161

Lost to Follow-Up

Subjects will be defined as lost to follow-up when the following procedures have been documented in the subject's source documentation:

- At least 2 phone calls made on separate dates to the subject are not returned
- A letter is sent to the subject's last known address and the subject does not reply after 30 days.

4. Informed Consent

Investigators are responsible for obtaining and documenting the voluntary informed consent of the study subjects prior to conducting any study-related assessments per 21 CFR Part 50. Prior to beginning the trial the investigator must obtain written and dated approval of the informed consent form. Subjects will receive a copy of the initial signed and dated informed consent form prior to the subjects' participation in the trial and any revised informed consent forms during the duration of the trial.

The subject must sign and date the consent form in the presence of the investigator, who must sign and date the consent form in the presence of the subject. The communications with the subject regarding informed consent process (initial and subsequent) should be documented in the medical record.

5. Study Procedures

Study Assessments

Visit 1- Baseline Assessment

The following information will be collected at the time of enrollment:

- Informed Consent
- Medical History & Demographics

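### Section 11.1 says 84 subjects allow for 20% drop-out from a minimum of 70, but 84 covers only 16.7%; at 20% about 67 remain

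*Combined protocol and SAP*

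**What the plan says.** Section 11.1 (Sample Size Estimate) bases the sample size on a global MANOVA test with 80% power at the 0.05 level: "we estimate the need for a minimum sample size of 70 for statistical significance (~35 per group"). The next sentence adds the allowance for losses: "To account for a 20% drop-out rate, a sample size of 84 subjects will be recruited". The Protocol Summary repeats 84, and Section 3 (Randomization) sets 1:1 allocation, so 42 per arm.

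Two other statements bear on what happens to drop-outs. Section 11.1 goes on to plan "intention to treat and a chains equation, multiple imputation method in which we will assign predictor", structural and imputed variables. Section 3.3, under voluntary withdrawal, says: "After a subject withdraws from the study, no effort will be made to replace or follow the subject".

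**The concern.** A drop-out rate is a share of those enrolled. If 70 are needed after losses and 20% are lost, the number to recruit is 70 divided by 0.80. The plan appears to have multiplied 70 by 1.20 instead, which gives too small an allowance.

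Section 11.1 does not call the 70 completers. But the allowance for drop-out is added on top of it, so it can only be the number meant to remain once losses have occurred. It is also described as a minimum, and only the per-group figure is marked as approximate.

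At stake is whether the plan gives the protection it claims. Under Section 3.3 those who withdraw are not replaced, so nothing in the conduct of the trial closes the gap, and their later outcomes are not collected.

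**Working it through.** **Inputs.** Minimum 70, drop-out 20%, recruited 84, power 80%, significance level 0.05, five outcome measures, two groups and an effect size of 0.20 are all from Section 11.1. The 1:1 allocation is from Section 3.

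**Reproducing the plan's 84.** 70 × (1 + 0.20) = 84 exactly. The usual inflation, n/(1 − d), gives 70/0.80 = 87.5, rounded up to 88, and does not return 84.

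**What 84 gives.**
- Left after a 20% loss: 84 × 0.80 = 67.2, which is 2.8 below 70.
- Per arm: 42 × 0.80 = 33.6, against about 35.
- Largest loss that keeps 70: 1 − 70/84 = 14/84 = 16.7%.
- Check on 88: 88 × 0.80 = 70.4.

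The 67.2 applies at the visit where the full 20% is missing. If losses build up over the 12 months, earlier visits lose fewer.

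**Effect on power.** This is conditional, because the plan assumes "2 groups and five outcome measures, and assuming an effect size of 0.20 (small) based on between group" differences without naming the metric. For a two-group global MANOVA test with p responses, power comes from the noncentral F distribution with df1 = p, df2 = N − p − 1 and noncentrality λ = N × f², at level 0.05. The figures are for completers only.

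| Assumed reading of 0.20 | Power at N = 70 | Power at N = 67 | Smallest N for 80% |
|---|---|---|---|
| f² = 0.20, p = 5 | 80.1% | 77.8% | 70 |
| f = 0.20 (f² = 0.04), p = 5 | 19.4% | 18.6% | 327 |
| f² = 0.20, p = 25 (5 scales × 5 time points) | 35.5% | 33.0% | 135 |

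Only the first row returns the plan's own 70. In all three rows, going from 70 to 67 costs about 1 to 2.5 percentage points.

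**The case against.** The strongest reply is that the plan does not analyse completers. It specifies intention to treat with chained-equations multiple imputation, so drop-outs stay in the analysis, and 84 only has to hold the information of 70 fully observed subjects.

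A rough calculation shows how much recovery that needs. Take one outcome at one visit, with data missing at random, and let R be the correlation between the missing score and its prediction from earlier observed scores. Then 1/Neff = (1 − R²)/67.2 + R²/84. With R = 0.3, Neff = 68.4; with R = 0.5, 70.7; with R = 0.6, 72.4. It reaches 70 at R² = 0.20, or R of about 0.45. With five scales measured at baseline and four follow-up visits, such a correlation is possible.

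This softens the consequence but does not make the sentence right. The documents give no correlations, so R is an assumption. Subjects lost early contribute only baseline data, and a finite number of imputations costs some precision. Above all, Section 11.1 takes no credit for imputation in arriving at 84: it offers that number purely as the allowance for a 20% loss. Had drop-out been treated as costless, no inflation above 70 would have been needed.

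It is also fair to say that the 20% is a round planning figure given without support, that no test or decision rule changes, and that the unnamed effect-size metric moves power far more than three subjects do. That last issue is separate. These points limit the weight of the error; they do not remove it.

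**Conclusion.** The concern holds. The three figures in Section 11.1 are inconsistent: 84 covers a 16.7% loss, not 20%, and at 20% about 67 subjects remain against a stated minimum of 70. This is plain arithmetic and does not depend on the effect-size metric or the missing-data method.

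The consequence is small: about 3 completers, and about 2 points of completers-only power (80.1% to 77.8%) if 0.20 means f² with five responses. On that reading 70 is the smallest number that reaches 80%, so there is no slack to absorb the shortfall. How much imputation would recover cannot be settled from the documents. The sentence should be corrected, but the error does not by itself call for a larger trial.

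**What to change.** Keep 84 and change the one sentence in Section 11.1. The preferable wording keeps the 20% expectation and discloses its result:

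> We will recruit 84 subjects (42 per arm). With 20% drop-out about 67 completers are expected, slightly fewer than the minimum of 70; drop-outs remain in the intention-to-treat analysis through multiple imputation.

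An alternative that is also true is to say that 84 allows for about 16.7% drop-out (14 of 84) while retaining 70 completers. It is the weaker choice, because the documents give no reason to expect 16.7% and the figure would be chosen only to fit 84.

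Any power figure added to the sentence should state the effect-size metric and the number of responses it assumes.

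The cost is one sentence. The Protocol Summary stands, and no extra patients, visits or data are needed.

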1 **A DOUBLE-BLIND, RANDOMIZED STUDY COMPARING STEROID INJECTION AND**
 2 **BIODRESTORE™ FOR PATIENTS WITH KNEE OSTEOARTHRITIS**

3
 4
 5
 6 **Protocol Summary**

Title of Study:	A Double-blind, Randomized Study Comparing Steroid Injection and BioDRestore for Patients with Knee Osteoarthritis
Study Type:	Postmarket Interventional
Primary Investigator:	[name]
Primary Endpoint:	Visual Analog Pain Score (VAS), VR-12, Lysholm, SANE and Knee Injury and Osteoarthritis Outcome Score (KOOS) at the 6-week, 3-month, 6-month, and 12-month post-injection time periods between the two groups.
Secondary Endpoints:	Inflammatory markers at 6 months post-injection.
Design:	Prospective, randomized, two-arm, double-blind study
Length of Study:	12M follow-up
Sample Size:	84 subjects

7
 8
 9 **Schedule of Events**

	BL	TX	6WK	3M	6M	12M
Informed Consent	√	-	-	-	-	-
Inclusion/ Exclusion	√	√	-	-	-	-
Demographics/ Medical History	√	-	-	-	-	-
Randomization	-	√	-	-	-	-
Physical Exam-ROM	√	-	√	√	√	√
Patient Outcomes (VAS, KOOS, Lysholm, SANE, VR-12)	√	-	√	√	√	√
Knee aspiration	-	√	-	-	√	-
X-ray	-	-	-	-	-	√
Adverse Event Assessment	√	√	√	√	√	√

11

12 **1. Background**

13

14 Osteoarthritis (OA), specifically involving the knee, is one of the most common causes of human disease¹
15 and can lead to significant pain and functional decline². A potential element of OA includes degenerative
16 tears of the knee meniscus and/or chondropathy, both of which involve destabilization from mechanical
17 or biological issues³.

18

19 Cortisone injections are commonly used to temporarily relieve inflammation and pain associated with
20 osteoarthritis. The response or effect of the injection can vary, depending on the stage of OA.⁴ Advanced
21 OA where little cartilage remains may not provide enough joint space for the injection to be effective.
22 Cortisone injections can also potentially cause an adverse reaction in certain patient populations,
23 particularly patients with diabetes who may experience a significant increase in blood sugar after a
24 cortisone injection.⁵

25

26 Alternatives to cortisone injections include viscosupplementation, platelet-rich plasma (PRP) injections
27 and stem-cell therapy. One form of therapy that has shown promising results with little reported on in
28 literature is amniotic tissue matrices, to include BioDRestore™ Elemental Tissue Matrix. BioDRestore is

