179 (prostaglandin-E₂; PGE₂) and soluble signals which indicate cartilage
180 damage (S100A8 and S100A9 proteins, respectively).
181
182 Briefly, frozen (-80°C) samples will be thawed and analyzed using a
183 bicinchoninic acid assay (BCA) to normalize for total protein content.
184 Samples will be diluted accordingly using calibrator diluent supplied with
185 ELISA kits. ELISA will be performed according to manufacturer's protocols
186 and well plates will be analyzed optically on a μ -Quant microplate reader.
187 Concentrations will be determined using a standard curve developed from
188 known concentrations of supplied analyte. Experimental sample analyte
189 concentrations (ng/ml) will be plotted on histograms and group mean
190 concentrations \pm standard deviation will be calculated for each experimental
191 group.
192 • **12-month only, subject will return to the clinic for the following:**
193 ○ Range of motion assessment
194 ○ Radiographs of affected knee
195 • **Allowed Concomitant Medications and Prohibited Treatments**
196 ○ Concomitant Medications: Patients are allowed acetaminophen and/or ibuprofen
197 for the first 6 months following treatment.
198 ○ Prohibited Treatments: Oral steroids, steroid injections and Viscosupplementation
199 are not permitted for the first 6 months of the study in the treated knee.
200

201 6. Risk Analysis

202 *Potential Risks*

203 Mild pain and discomfort at the injection site are normal and expected reactions. While
204 rare, complications may occur due to either the cortisone injection or study injection.

205 These include the following:

- 206 • Infection
- 207 • Post-injection flare
- 208 • Localized subcutaneous or cutaneous atrophy
- 209 • Skin discoloration
- 210 • Stiffness

211
212
213
214
215
216
217
218
219
220
221
222
223
224
225
226
227
228
229
230
231
232
233
234
235
236
237
238
239
240
241
242
243
244
245
246
247
248
249
250
251
252
253
254
255
256
257
258

Potential Benefits

Participation in this study may offer no benefit to subjects. However, it is possible that the use of BioDRestore will result in better outcomes than corticosteroid when injected intra-articularly in patients with knee OA.

Study subjects will receive a \$50 stipend for each study visit for a total of \$300 if all visits are completed.

7. Adverse Events

Definitions

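### Five scales at four visits form one unranked primary endpoint, and section 11.2 does not say which MANOVA decides the trial or what result counts as success

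*Combined protocol and SAP*

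**What the plan says.** **Endpoint.** The Protocol Summary and section 2 give one primary endpoint that begins "Visual Analog Pain Score (VAS), VR-12, Lysholm, SANE and Knee Injury and Osteoarthritis Outcome Score (KOOS) at the 6-week" and continues through 3, 6 and 12 months. Five scales at four visits make 20 scale-by-visit comparisons. None is ranked above another.

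**Hypothesis.** Section 1 expects BioDRestore to give "better outcomes than corticosteroid when injected intra-articularly in patients with knee OA". This is directional, but no scale or visit is attached to it.

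**Sizing.** Section 11.1 describes the setting as "Assuming normal distributions among the 2 independent groups' 5 time-points for" "2 groups and five outcome measures, and assuming an effect size of 0.20 (small) based on between group" differences, and the aim as "Measuring global effects, with an expected 80% power, and a standard error of probability" of 0.05. The result is 70 subjects, about 35 per group, raised to 84 for drop-out.

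**Analysis.** Section 11.2 says a MANOVA will "be used to measure differences between the targeted outcome measure at each of the given timepoints", and lists baseline, 6 weeks, 3, 6 and 12 months. It explains that MANOVA relates the group factor to a vector of correlated outcomes. For all analyses, a p value of "<0.05 will be considered statistically significant". No section names a lead test, a success rule or a multiplicity adjustment.

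**The concern.** Section 11.2 names a method but not a test. Three readings are open:

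- **Per visit:** one MANOVA of the five scales at each timepoint. This gives five tests as listed, or four if baseline is left out.
- **Per scale:** one MANOVA for each scale, with the timepoints as the response vector. This gives five tests, and the singular wording for the outcome measure supports it.
- **Global:** a single test, as the reference to global effects in section 11.1 suggests.

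These can give different answers on the same data. With nothing prespecified, the analysis that decides the trial can be picked once results are known, and the 0.05 used for sizing need not be the trial's error rate.

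Direction is a second gap. MANOVA detects any difference between the group mean vectors, including one that favours corticosteroid or one that is mixed across scales. The plan does not say what pattern of scale results would support the hypothesis.

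**Working it through.** **Inputs.** From section 11.1: two groups, five outcome measures, five timepoints, effect size 0.20 (metric not named), alpha 0.05, power 80%, N = 70. From section 3: 1:1 allocation. From section 11.2: five timepoints, 0.05 throughout. The documents give no correlations, so 0.3 to 0.7 is assumed.

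**Step 1: reproduce 70.** For a two-group MANOVA with p responses, the test is F on p and N − p − 1 degrees of freedom, with noncentrality λ = N × f².

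- p = 5, f² = 0.20, N = 70: df 5 and 64, λ = 70 × 0.20 = 14.0, power 0.801.
- N = 69: λ = 13.8, power 0.794.

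So 70 is the smallest N that reaches 80% for this test.

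**Step 2: does 70 identify the test?** It does not.

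- A MANOVA with four responses and the convention λ = (N − p − 1) × f² also gives 70: λ = 65 × 0.20 = 13.0, power 0.806 (0.798 at N = 69).
- A repeated-measures group-by-time F test with f = 0.20, m = 4 measurements and correlation ρ = 0 also gives 70: λ = f² × N × m / (1 − ρ) = 0.04 × 70 × 4 = 11.2 on 3 and 204 df, power 0.803 (0.797 at N = 69).
- Even on the five-response reading, the five could be the scales or the timepoints.
- The f-squared reading fits poorly with the plan's own description of the effect as small. With equal groups D² = 4f² = 0.80, so the Mahalanobis distance is √0.80 = 0.89. If 0.20 were f instead (f² = 0.04), a five-response MANOVA would need 327.

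**Step 3: chance of at least one false positive if any significant test counts.** With independent tests it is 1 − 0.95⁴ = 0.185 for four and 1 − 0.95⁵ = 0.226 for five. With correlated tests it was simulated under a true null: normal data, 35 per group, Hotelling's T², equal correlations. There were 40,000 trials per setting for the first and third rows and 20,000 for the second.

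| Reading | Correlation between tests 0.3 | 0.5 | 0.7 |
|---|---|---|---|
| Four post-injection visits | 18% | 16% | 14% |
| Five visits, baseline included | 21% | 20% | 16% |
| Five scales | 21% | 19% | 16% |

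The second row is quoted elsewhere as about 15–22%, to leave room for simulation error. A single five-scale MANOVA at one visit gave 5%.

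**The case against.** The strongest defence is that section 11.1 sizes a global effect at one alpha and section 11.2 describes a vector of outcomes. The authors may therefore intend a single global test, which would hold 5%. No section says that any significant result wins. This is fair, and it has two consequences.

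First, a reader might infer that the trial's false-positive rate is 14–22%. The documents do not support that. The figures need two additions to the text: a per-visit or per-scale reading, and a rule that any significant test counts. They also depend on the rule chosen. If success required a significant MANOVA plus at least one unadjusted comparison favouring BioDRestore, the rate would be about 5–8% per visit and 6–10% per scale, against about 2% for one named visit under the same rule. That rule is not in the plan either.

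Second, a reader might infer from the exact match at 70 that one five-response MANOVA was sized and must be the primary test. Step 2 rules that out, because other tests and another metric give the same number.

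The defence does not close the gap. Section 11.2 never names a global test, its wording points to separate analyses by timepoint, and its significance threshold applies to all of them. Nor would a global test by itself show that BioDRestore is better.

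**Conclusion.** The point stands, and it should be fixed before unblinding. What is established from the text alone is that the primary endpoint is unranked and that neither the deciding MANOVA, its response vector nor the success rule is stated. The sample size does not settle which test was meant.

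The error rates are conditional illustrations: about 14–18% (four visits), 15–22% (five visits with baseline) and 16–21% (five scales). They assume a true null, normal data, 35 per group, correlations of 0.7 down to 0.3, and an any-test-wins rule that the plan neither states nor excludes. The conclusion that the decision rule is open does not depend on them.

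**What to change.** Amend sections 2 and 11.2 before unblinding:

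- Name one primary between-group MANOVA of the five scales, at one named post-injection visit, at two-sided 0.05. The sponsor should choose and justify the visit. Six months is one option: it is the last visit inside the period in which the treatments listed as prohibited in section 5 "are not permitted for the first 6 months of the study in the treated knee".
- Make all other visits secondary, and remove baseline from the tested timepoints.
- Test individual scales only if the primary test is significant, with Holm adjustment across the five. Report the direction of each, and claim superiority only on scales that favour BioDRestore.

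In section 11.1, state which effect-size metric 0.20 is and which responses were sized.

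**Cost.** Wording only: N, visits and data collection are unchanged. The downside is that results at the visits not chosen become secondary, so an effect confined to one of them could not carry the trial's main conclusion.
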